1.6. Summary of Benefits and Risks

Based on the available nonclinical data, the risks and potential benefits for PF-06835375 are considered to be favorable and support clinical development in subjects with SLE and RA.

SLE and RA both have higher prevalence in females and hence the trial objectives cannot be met without inclusion of women of childbearing potential (WoCBP). Nonclinical data to date (Section 1.2.6) have not identified any risk to reproductive organs in sexually mature cynomolgus monkeys, the pharmacologically relevant species. Given that an enhanced pre- and postnatal development study (ePPND) will be conducted later in development, this protocol that allows enrollment of WoCBP has stringent requirements to mitigate unintended exposures (pregnancy testing and use of contraceptives; see Section 4.4.1). Subjects will be followed for a minimum of 16 weeks after Day 1 during the study, which extends beyond predicted drug exposure of five half-lives based on expected PK.

Based on studies with other B cell and T cell depleting agents, there is a dose-dependent risk for infusion and injection reactions with PF-06835375, potentially severe. Subjects will be closely monitored for 8-12 hours post-infusion as per Schedule of Activities. As described in Section 5, subjects will be pre-medicated to mitigate this risk, and peri- and post-infusion medications to manage infusion and/or injection reactions will be available for subjects receiving IP.

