- In Part A, for cohorts A1-A4 (with 4 subjects planned), 4 subjects have completed two weeks post-dose in the study. In Part A, for Cohorts A5-A8 and B1-B5 (with 8 subjects planned), 6 subjects must complete two weeks post-dose in the study.
- The majority of subjects dosed with PF-06835375 in a given cohort have a detectable B cell count (obtained from the CLIA certified central lab; LLOQ = 1 B cell per μ L of blood) for a minimum of 2 consecutive visits at least 2 weeks apart, starting at Week 12. Subjects, who reach detectable B cell counts and withdraw from the study earlier, will be considered as having met this criterion. Subjects who withdraw from the study prior to reaching a detectable B cell count will not be counted in the cohort size (this will be limited to 1 subject per cohort of 4 or 2 subjects per cohort of 8). Investigators will have access only to de-identified B-cell count data to remain blinded.
- The sponsor and majority of investigators with active subjects and/or subjects enrolled in the dose level under review (includes only subjects who received IP) agree to proceed to the next dose level based on the overall safety profile. For the purpose of defining the majority of investigators, only one investigator from each site will be counted.

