3.4.2. Dose Escalation Stopping Rules

Dose escalation stopping rules will be used to determine whether the maximal tolerated dose has been attained. Dose escalation will be stopped if it is determined that the limits of safety and/or tolerability have been reached based on the criteria described in this section. This decision will be made after a discussion takes place between the sponsor study team and the investigator. The sponsor study team may not overrule the investigator's decision to stop dose escalation. If dose escalation is stopped because of any of these criteria, additional cohorts may receive the same or lower doses of the investigational product.

The dose escalation will be terminated based on the following criteria:

- If ≥ 2 subjects within a dose cohort develop *Common Terminology Criteria for Adverse Events* (CTCAE) v4.0 Grade 3 adverse event considered to be serious (ie, SAE) in the same organ system, or if 1 subject develops a CTCAE v4.0 Grade 4 or higher SAE, considered related to study drug, and not clearly related to the underlying disease (ie SLE or RA) process, concomitant medications or supplements.
- Laboratory abnormalities known to be associated with B-cell depleting therapies (neutropenia, thrombocytopenia and anemia) will not be considered for this criterion, instead these laboratory abnormalities will be considered for Individual Stopping Rules ([Section 3.4.3](#)).
- If 50% or more subjects within a dose cohort experience a CTCAE v4.0 Grade 3 or higher infusion reaction as defined by the criteria in [Appendix 7](#).
- If a confirmed or probable case of Progressive Multifocal Leukoencephalopathy is observed, the sponsor will hold dosing for all subjects until the benefit risk assessment of PF-06835375 is re-evaluated by the sponsor (See [Section 7.1.14](#)). If the sponsor concludes the benefit risk assessment is favorable, investigators will be consulted on whether to proceed as described in this section.
- If, at any dose level, the mean exposure for the treatment group reaches or exceeds the exposure stopping limit of C_{av} of 261 $\mu\text{g}/\text{mL}$, OR, based on the observed data, the group mean C_{av} of the next planned dose is projected to exceed the exposure stopping limit (See [Section 1.3](#)). Modified doses may be explored if they are not expected to exceed PK stopping criteria.

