If any dose cohort is repeated, this additional cohort will be considered a separate cohort for the purpose of this dose escalation stopping rules.

To determine whether any of the above criteria for stopping dose escalation have been met, the sponsor will convene a dose review team meeting between the sponsor (including at minimum Medical Monitor or Clinical Lead, Clinical Pharmacologist and Statistician) and Investigators who have active subjects or who enrolled in the dose cohort under review, to review adverse event(s) and all relevant safety data. This meeting may take place as part of standard dose escalation meeting or ad-hoc based on emerging safety data. Unblinding to determine relatedness to investigational product may be considered.

If any of the above criteria is considered to have been met as determined by unanimous decision of the dose review team members OR if a unanimous decision cannot be reached:

- No further doses should be administered at this dose and no dose escalation will proceed.

- Enrollment of the study may continue at a lower dose or a lower dose cohort may be added to the study.

Otherwise, upon unanimous decision of the dose review team members that it is safe to proceed, one of the following decisions may be made by the sponsor:

- Enrollment of the cohort may resume as planned.
- The cohort may be expanded at the same dose.
- Enrollment of the study may continue at a lower dose or a lower dose cohort may be added to the study.

Unanimous decision is defined as all Investigators who have active subjects or enrolled in the dose cohort under review (one Investigator per site) and sponsor medical representative (medical monitor or clinical lead) agree.

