Cytokine release syndrome/acute infusion reaction	Cytokine release	Mild reaction; infusion interruption not indicated; intervention not indicated	Requires therapy or infusion interruption but responds promptly to symptomatic treatment (eg, antihistamines, NSAIDS, narcotics, IV fluids); prophylactic medications indicated for ≤ 24 hrs	Prolonged (ie, not rapidly responsive to symptomatic medication and/or brief interruption of infusion); recurrence of symptoms following initial improvement; hospitalization indicated for other clinical sequelae (eg, renal impairment, pulmonary infiltrates)	Life-threatening; pressor or ventilatory support indicated	Death

Remark: Cytokine release syndromes/acute infusion reactions are different from Allergic/hypersensitive reactions, although some of the manifestations are common to both AEs. An acute infusion reaction may occur with an agent that causes cytokine release (eg, monoclonal antibodies or other biological agents). Signs and symptoms usually develop during or shortly after drug infusion and generally resolve completely within 24 hrs of completion of infusion. Signs/symptoms may include: Allergic reaction/hypersensitivity (including drug fever); Arthralgia (joint pain); Bronchospasm; Cough; Dizziness; Dyspnea (shortness of breath); Fatigue (asthenia, lethargy, malaise); Headache; Hypertension; Hypotension; Myalgia (muscle pain); Nausea; Pruritis/itching; Rash/desquamation; Rigors/chills; Sweating (diaphoresis); Tachycardia; Tumor pain (onset or exacerbation of tumor pain due to treatment); Urticaria (hives, welts, wheals); Vomiting.

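### Cheap improvement: placebo subjects count in the 50% infusion-reaction stop, so a full 6:2 IV cohort needs 4 of 6 exposed reactors (67%) to trigger it

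*Protocol*

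**What the plan says.** Protocol 3.4.2 gives the purpose of the rules: "Dose escalation stopping rules will be used to determine whether the maximal tolerated dose has been attained". One rule stops escalation "If 50% or more subjects within a dose cohort experience a CTCAE v4.0 Grade 3 or higher infusion reaction", graded by Appendix 7. The rule does not limit the denominator to subjects on active drug. Protocol 4.3 randomizes to drug or placebo within each cohort, and Table 2 sets A1 to A4 at three active and one placebo, and A5 to A8 at six active and two placebo.

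Elsewhere the protocol does name a narrower group when it means one. The B-cell criterion in 3.4.1 is limited to subjects dosed with PF-06835375, and the exposure limit in 3.4.2 refers to the treatment group.

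The other numeric clinical stop in 3.4.2 needs serious events: two or more subjects with a "Grade 3 adverse event considered to be serious (ie, SAE) in the same organ system", or one subject with a related Grade 4 or higher SAE.

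Three further provisions rest on judgment:
- Escalation needs agreement from "The sponsor and majority of investigators with active subjects and/or subjects enrolled in the dose level under review" (3.4.1).
- The sponsor may not overrule an investigator who decides to stop (3.4.2).
- Dosing at that level and escalation stop if a criterion is judged met "OR if a unanimous decision cannot be reached" (3.4.2).

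**The concern.** Placebo subjects cannot have a drug-caused reaction, so including them mainly dilutes the percentage. A limit that reads as 50% becomes 67% of those at risk in a full 6:2 cohort.

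The hazard is foreseen. Protocol 1.6 says "there is a dose-dependent risk for infusion and injection reactions with PF-06835375, potentially severe", and 1.2.6 reports cytokine release in vitro with human cells. The 6:2 IV cohorts are also the higher-dose IV cohorts.

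This is the only numeric cohort-level rule for Grade 3 infusion reactions that are not serious. Such reactions are possible: Grade 3 in the cytokine release row of Appendix 7 includes prolonged symptoms and "recurrence of symptoms following initial improvement", and Protocol 8.3 separates severity from seriousness. With half of the exposed subjects reacting in this way, the dose review would start from a rule that reads as not met.

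**Working it through.** **Inputs.** The 50% limit and its denominator are from 3.4.2. Allocation is from Table 2. The minimum of six dosed, including at least one placebo, is from 3.4.1. Cohorts as run are from SAP Table 1. The documents give no reaction rate, serious fraction or operating characteristics for this rule, so there is no plan figure to reproduce beyond the implied count. All rates below are assumptions.

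**Step 1: reactors needed.** As written, the trigger is half of all subjects dosed, rounded up. Exposed-only, it is half of the active subjects dosed, rounded up. No placebo reactions are assumed.

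| Dosed | As written | Exposed-only |
|---|---|---|
| 6 active + 2 placebo | 4 (67% of exposed) | 3 (50%) |
| 6 active + 1 placebo | 4 (67%) | 3 (50%) |
| 5 active + 2 placebo | 4 (80%) | 3 (60%) |
| 4 active + 2 placebo | 3 (75%) | 2 (50%) |
| 5 active + 1 placebo | 3 (60%) | 3 (60%) |
| 3 active + 1 placebo | 2 (67%) | 2 (67%) |

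Three reactors in a full 6:2 cohort are 3/8 = 37.5%, below the limit. The 3:1 cohorts, and a review at five active plus one placebo, do not change. The partial rows read the denominator as subjects dosed so far, which 3.4.2 does not specify.

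**Step 2: this rule alone, full 6:2 cohort.** With X ~ Bin(6, p), compare P(X ≥ 4) as written with P(X ≥ 3) exposed-only.

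| True exposed rate p | As written | Exposed-only |
|---|---|---|
| 0.2 | 0.017 | 0.099 |
| 0.3 | 0.070 | 0.256 |
| 0.4 | 0.179 | 0.456 |
| 0.5 | 0.344 | 0.656 |
| 0.6 | 0.544 | 0.821 |

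If placebo subjects react at 5% or 10%, the written rule at p = 0.5 fires with probability 0.375 or 0.405.

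**Step 3: add the SAE rules.** The two versions differ only when exactly three exposed subjects react and no SAE rule fires. Let s be the serious fraction of Grade 3 reactions and g the fraction of reactions that are Grade 4. Assume that all reactions are related, that all are in one organ system, and that every Grade 4 reaction is an SAE. Then:

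gap = P(X = 3) × (1 − g)³ × P(Bin(3, s) ≤ 1)

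At p = 0.5, P(X = 3) = 20/64 = 0.3125.

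| s | g | Gap | At least one numeric rule fires: as written vs exposed-only |
|---|---|---|---|
| 0 | 0 | 0.3125 | 0.344 vs 0.656 |
| 0.3 | 0 | 0.3125 × 0.784 = 0.245 | 0.432 vs 0.677 |
| 0.5 | 0 | 0.3125 × 0.5 = 0.156 | 0.559 vs 0.715 |
| 0.5 | 0.1 | 0.3125 × 0.729 × 0.5 = 0.114 | 0.644 vs 0.758 |
| 0.7 | 0.1 | 0.3125 × 0.729 × 0.216 = 0.049 | 0.754 vs 0.803 |
| 1 | 0 | 0 | 0.891 vs 0.891 |

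Reactions spread over several organ systems would weaken the SAE rule and widen these gaps.

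**The case against.** The strongest case is that this is a preference about a threshold. Nothing in the documents says that the intended limit is 50% of exposed subjects. Because the protocol names the narrower group where it wants it, counting everyone may be deliberate: blinded investigators can then apply the rule without treatment codes. That stands, and it is why this is not an error. A reader might infer that the rule contradicts the protocol's stated purpose. The documents do not support that, since they set no target rate against which 4 of 6 would be wrong.

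A reader might also infer that three reactors in six would go unnoticed, or that escalation would then proceed. That does not follow. The escalation meeting reviews infusion reactions (3.4.1), named sponsor staff are unblinded (SAP section 3), and one dissenting investigator is enough to stop. What remains is that all of these are judgments.

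Third, the 31-point gap overstates the effect. Appendix 7 Grade 4 includes anaphylaxis and life-threatening reactions, and one related Grade 4 SAE stops escalation. Some Grade 3 descriptions, such as symptomatic bronchospasm or an indication for hospitalization, overlap with the SAE definition and its examples in 8.2.3. This stands: 31 points applies only if no reaction is serious.

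Finally, the scope is narrow. The only IV escalation that followed a 6:2 cohort was A5 to A6, since A7 and A8 were not used. The documents do not show that any escalation decision was affected.

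**Conclusion.** The point holds as an optional-to-recommended, low-cost improvement. In a full 6:2 IV cohort with no placebo reactor, the rule needs 4 of 6 exposed reactors instead of 3. The other numeric rules narrow the gap but close it only if they catch every case of three reactors, for example when all reactions are serious and in one organ system.

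At an assumed 50% exposed rate, with all reactions related and in one organ system, the difference in the chance that some numeric rule fires is about 24 points with 30% serious and 16 with half serious, ignoring Grade 4 in both. It is about 11 points with 10% Grade 4 and half of the Grade 3 reactions serious, and about 5 with 10% Grade 4 and 70% serious. The difference in actual stopping would be smaller, because sponsor and investigators can also stop. As run, the scope is A5 and A6. SAP Table 1 lists every Part B cohort as SC.

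**What to change.** Either of two one-phrase changes to 3.4.2 would do.

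**Percentage form.** Make the denominator subjects dosed with PF-06835375 within the cohort. The already unblinded sponsor personnel count, and report to the dose review team only whether the rule is met. The cost is some disclosure and dependence. At three reactors in eight, a report of met tells sites that all three had active drug, and not met tells them that at least one had placebo. Investigators can no longer apply the rule themselves. Two active plus two placebo reactors would no longer trigger it. The disclosure is limited: after met, escalation has stopped; not met does not identify a subject; and 3.4.2 already says "Unblinding to determine relatedness to investigational product may be considered".

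**Count form.** State the trigger as three or more subjects in an 8-subject cohort and two or more in a 4-subject cohort. This needs no treatment codes, so it leaks nothing, and it does not depend on how many placebo subjects have been dosed. It would need restating if a cohort is enlarged, which Table 2 allows. With only four active subjects dosed it is less strict than the percentage form (three against two).

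Both forms stop more often at lower true rates. With no placebo reactions, a full 6:2 cohort triggers the rule in 10% against 2% at a true rate of 20%, and in 26% against 7% at 30%.

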1.2.6. Nonclinical Safety

Administration of PF-06835375 once every two weeks by IV bolus or SC injection for up to 2 months in cynomolgus monkeys resulted in dose-independent depletion (maximum pharmacology reached at the lowest dose) of total B cells and cTfh/Tfh cells in the peripheral blood and spleen, and was associated with decreases in total lymphocyte and white blood cell counts and decreased lymphoid follicular cellularity in the spleen, lymph nodes and gut-associated lymphoid tissue for the dose range tested (5-200 mg/kg/dose). These changes were nonadverse, partially to fully reversible, and consistent with the expected pharmacology of PF-06835375. PF-06835375 did elicit cytokine release in the in vitro soluble and solid phase cytokine release assay using human whole blood or peripheral blood mononuclear cells (PBMCs), however, cytokine release was not detected in the repeat-dose toxicity studies in cynomolgus monkeys. At a SC dose of 20 mg/kg/dose, there were no local injection site reactions. Reproductive and developmental toxicity studies have not been conducted, but there were no findings in male and female reproductive tissues evaluated in the repeat-dose toxicity studies. The no observed adverse effect level (NOAEL) was 200 mg/kg/dose IV, the highest dose tested, which was associated with systemic exposure of 5220 μ g/mL (C_{max}) and 438,000 μ g•h/mL (AUC_{168}).

Additional information for PF-06835375 may be found in the single reference safety document (SRSD), which for this study is the current Investigator's Brochure.

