3.2. Sentinel Dosing

In view of the mechanism of action (B cell and cTfh cell depletion), the interval between sentinel subjects and the remainder of the cohort is proposed to mitigate any unanticipated acute safety risks (ie, infusion/injection site reactions). Sentinel dosing will be employed as follows:

- In Part A, for Cohorts A1-A4 (with 4 subjects planned), subjects will be dosed IV at least 24 hours apart. In order to avoid investigator unblinding, the one subject on placebo in these cohorts may be enrolled in any sequence. The sponsor medical monitor will communicate with investigator(s) from each site after dosing of each subject (and prior to dosing of the next subject) in order to determine whether it is safe to proceed with continued dosing within a cohort.

If the sponsor decides to increase the number of subjects in these A1-A4 cohorts, the sentinel dosing will apply only to the first four subjects as described in the paragraph above. After the sponsor medical monitor determines it is safe to proceed, the remaining subjects can be enrolled and dosed simultaneously.

- In Part A, for cohorts A5-A8 (with more than 4 subjects planned), the first two subjects dosed IV will include one PF-06835375 and one placebo subject. If safety and tolerability profile is acceptable in these two subjects, dosing of additional subjects can occur 24 hours after dosing of the first two subjects. These additional subjects within a cohort may be enrolled and dosed simultaneously. The determination to proceed with dosing of additional subjects will be made by the sponsor following communication between sponsor medical monitor and investigator(s) from sites which enrolled sentinel subjects.
- In Part B, for all SC cohorts, sentinel dosing for the first two subjects (as described for Cohort A5-A8 above) will only be employed if a given SC dose level (or higher) was not previously tested in Part A using the IV route of administration. For example, if Cohort A4 (single 1 mg IV dose) has not been tested, sentinel dosing will be used in Cohort B2 (two SC doses of 1 mg). If safety and tolerability profile is acceptable in two subjects after the first of two doses, dosing of additional subjects can occur 24 hours after dosing of the first two subjects.

If in Part B the SC bioavailability is low and the decision is made to change the route of administration to IV, then sentinel dosing in Part B will not be repeated for dose levels already administered in Part A.

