3.4. Dose Escalation and Stopping Rules

3.4.1. Dose Escalation

The decision to progress to the next higher dose in Parts A and B will be made following the review of available safety/tolerability, PK and PD data for the preceding dose levels (in a respective Part) and after the sponsor (Medical Monitor, Clinical Pharmacologist and Study Statistician at a minimum) and investigators (with active subjects or subjects enrolled in the dose level under review) determine that it is safe to proceed to the next dose level.

Once Part B has been initiated, dosing in subsequent cohorts in Part B may occur either via SC or IV routes. Specific criteria for dose escalation in Part B are provided below:

- SC route of administration in Part B: dose escalation in SC cohorts in Part B may occur independent of IV cohorts in Part A.
- IV route of administration in Part B: dose escalation in Part B will only occur after subjects have been dosed with a three-fold higher IV dose in Part A. For example, dosing in B2 (two 1 mg IV doses) may commence after dosing in Cohort A5 (single 3 mg IV dose) occurred.

If the decision has been made to dose escalate, it is at sponsor's discretion whether to proceed with dose escalation. It is also at sponsor's discretion whether to repeat the same dose or to test a lower dose based on emerging data. The dose escalation meeting will review infusion and injection site reactions, and the sponsor will provide guidance to Investigators on management of injection/infusion reactions in the subsequent cohort, including the need for pre-medication with corticosteroids.

Review of ongoing safety data will continue after dose escalation has either been completed or stopped and subjects remain active in the study. These meetings will include a similar group as the dose escalation meetings, and will be scheduled every three months at a minimum.

Dose escalation can proceed after the following criteria are met:

- For cohorts with 4 planned subjects, all 4 subjects have been dosed. For cohorts with 8 planned subjects, at least 6 subjects have been dosed, including at least one placebo subject.
- Sponsor medical monitor and investigators who enrolled subjects in a given cohort have reviewed all available safety data for dosed subjects, including:
 - minimum of 2 weeks of safety and tolerability data after the last study drug dose, AND
 - minimum 1 week of PK data after the last study drug dose.

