8.3.4. Adverse Events

Adverse events will be reported in accordance with the sponsor reporting standards. Several minor ad-hoc adjustments and additions will be conducted.

In the case report forms (CRF) the infusion-related adverse effect was characterized by toxicity grade, instead of the conventional characterization of the AE by severity. The possible toxicity grades are 0,1,2,3,4. The values of toxicity grades = 0, 1, 2 will be mapped to the “mild” category of the AE severity score and values of the toxicity score equal to 3 and 4 will be mapped to the “moderate” and “severe” scores accordingly. The explanation of this mapping from toxicity to severity scale needs to be included into the footnote of the otherwise standard summaries of the adverse events.

Listings with the descriptions of infusion-related reactions (IRR) and injection site reactions (ISR) will be created (separately for all causalities and treatment related adverse events) with the description of individual adverse effects.

Similar listings describing subsets of all events of participants who had preferred term of a special interest that may suggest the occurrence of cytokine release syndrome, with start on Day 1-3 after dose 1 (IV or SC) or Day 1- 4 after dose 2 (SC) will be created (separately for all causalities and treatment related adverse events). The set of preferred term of interest will include tachycardia, hypotension, hypertension, chills, vomiting, nausea, headache, pyrexia, dizziness, and palpitations. The observation of a group of two or more events from this set within a short time window after the dosing will be viewed as a potential cytokine release syndrome event (PCRE). The tabulation showing total number of participants and number and percent of PCREs within each of the doses will be created. Note that this analysis is exploratory and the list of preferred terms may be modified if needed.

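### The 50% / Grade 3+ reaction criterion for stopping escalation names infusion reactions only, so as worded it does not reach the subcutaneous cohorts planned for Part B

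*Protocol*

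**What the plan says.** Protocol 3.4.2 presents its criteria as the means of deciding whether the maximal tolerated dose has been reached. Only one of them is a reaction rate: escalation ends if 50% or more "subjects within a dose cohort experience a CTCAE v4.0 Grade 3 or higher infusion reaction", as defined in Appendix 7. That appendix is titled for infusion reactions. Section 7.1.12 sorts infusion reactions into acute, immediate and late, with the first two windows tied to the infusion.

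Reactions to SC dosing are handled separately. Section 7.1.13 covers injection site reactions and sends them to Appendix 8, which grades local pain, tenderness, redness and swelling on its own intensity scale, not by CTCAE grade.

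Protocol Table 2 plans SC for B1-B5 and for optional X6. The route may be changed for all of these except B1, and 3.3 requires the first Part B dose to be SC. Section 3.4.1 adds that "dose escalation in SC cohorts in Part B may occur independent of IV cohorts in Part A". It also provides that "The dose escalation meeting will review infusion and injection site reactions", but attaches no threshold to that review.

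On the risk itself, 1.6 says that "there is a dose-dependent risk for infusion and injection reactions with PF-06835375, potentially severe". Section 1.2.6 reports that "PF-06835375 did elicit cytokine release in the in vitro soluble and solid phase cytokine release assay", and goes on to say that no cytokine release was detected in the repeat-dose monkey studies.

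**The concern.** The same reaction pattern is treated differently by route. If half of an IV cohort has Grade 3 rigors, high fever or recurrent symptoms, a stated criterion is met. If half of an SC cohort has the same, and none of the events is classed as serious, no criterion in 3.4.2 is met. The decision then rests on the general safety review in 3.4.1.

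The protocol gives no reason for exempting SC, and 1.6 names injection reactions alongside infusion reactions. Because SC cohorts may escalate without waiting for IV cohorts, the IV criterion cannot be relied on to act for them. At stake is whether a rule meant to identify the maximal tolerated dose applies to the route planned for all of Part B.

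**Working it through.** **1. Which cohort-level criteria in 3.4.2 could catch non-serious Grade 3 systemic reactions in an SC cohort?**

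| Criterion | Any route? | Counts non-serious Grade 3 systemic reactions? |
|---|---|---|
| Related SAEs: Grade 3 in 2 or more subjects, same organ system, or one of Grade 4 or higher | Yes | No, it requires an SAE |
| 50% with Grade 3+ infusion reaction | Worded for infusion | Yes, but only after an infusion |
| Confirmed or probable PML | Yes | No |
| Mean exposure at or above the C_av limit | Yes | No |

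Appendix 7 shows which events are involved. Its Grade 3 column includes severe or prolonged rigors, fever above 40.0°C for up to 24 hours, and symptoms that recur after improving. These can occur without meeting an SAE definition. Other Grade 3 entries, such as those where hospitalization is indicated, would normally be SAEs and are already covered.

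**2. Planned subjects affected (Protocol Table 2).**

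- A1-A4: 4 × 4 = 16. A5-A8: 4 × 8 = 32. B1-B5: 5 × 8 = 40. X6: up to 24.
- Total: 16 + 32 + 40 + 24 = 112, which reproduces the stated enrolment of approximately 112.
- SC without X6: 40 / (48 + 40) = 40/88 = 45%.
- Active subjects without X6: SC 5 × 6 = 30; Part A 4 × 3 + 4 × 6 = 36; 30/66 = 45%.

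**3. What the criterion requires.**

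- Full cohort of 8 (6 active, 2 placebo): 0.5 × 8 = 4 subjects. If only active subjects react, that is 4/6 = 67% of them.
- At the minimum of 6 dosed subjects in 3.4.1, with at least one on placebo: 0.5 × 6 = 3, which is 3/5 = 60% or 3/4 = 75% of active subjects.

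**4. How often it would fire in a full cohort of 8.** The documents give no reaction rates, so the rates p below are assumptions. Placebo reactions are taken as zero, and X ~ Binomial(6, p).

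P(X ≥ 4) = 15p⁴(1−p)² + 6p⁵(1−p) + p⁶

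| Assumed active-arm rate | Criterion applies | SC cohort, literal wording |
|---|---|---|
| 30% | 0.07 | 0 |
| 50% | 0.34 | 0 |
| 70% | 0.74 | 0 |
| 80% | 0.90 | 0 |

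At 50%, for example, (15 + 6 + 1)/64 = 22/64 = 0.34.

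**The case against.** There is a good case that this matters little.

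- **Lower peak exposure.** Protocol Table 1 predicts an SC C_max of about a quarter of that for the same IV dose (3 mg: 0.32 against 1.24 µg/mL; 10 mg: 1.08 against 4.2). This makes a trigger less likely. It is not a stated reason for exempting SC.
- **Seriousness is broad.** Section 8.2.3 makes important medical events serious, and 8.1 lets the sponsor reclassify a non-serious event as serious. Many Grade 3 reactions could therefore fall under the SAE rule, which two subjects can trigger. This stands and narrows the gap, but it depends on case-by-case judgement.
- **Other controls apply to SC.** A Grade 3 event that prevents daily activity and needs intervention, or any SAE, bars the second dose (3.4.3). Escalation needs agreement from the sponsor and a majority of investigators. The sponsor may not overrule an investigator's decision to stop. All subjects are premedicated. These stand too, although a bar on dose 2 cannot act on reactions to dose 2 and does not itself stop escalation.
- **Sentinel dosing** helps only in part. It applies "if a given SC dose level (or higher) was not previously tested in Part A using the IV route of administration", involves one active and one placebo subject, and looks at the first dose only: "If safety and tolerability profile is acceptable in two subjects after the first of two doses".
- **The IV criterion is not automatic.** The dose review team decides whether it is met, though failure to agree unanimously defaults to stopping.

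Two stronger readings are tempting. A reader might infer that SC cohorts have no stopping rule; the controls above show otherwise. A reader might also take the SAP 8.3.4 search for possible cytokine release after SC doses as proof that such reactions were foreseen when the rule was written. The documents do not support that. SAP section 1 lists the search as an addition, the same SAP version already records actual doses and unused cohorts, and 8.3.4 calls the analysis exploratory. It shows only that the sponsor came to regard such reactions as relevant.

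**Conclusion.** The point holds on the wording, as a minor gap. The 50% / Grade 3+ criterion does not literally reach the SC cohorts B1-B5, which hold 40 of 88 planned subjects without X6. What is left uncovered is non-serious Grade 3 systemic reactions in half or more of an SC cohort. Support comes from 1.6, which expects potentially severe injection as well as infusion reactions, and more weakly from the in vitro finding in 1.2.6, which the monkey studies did not bear out.

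A reader might quote 64 of 112 subjects (57%) as affected. That needs X6 to be filled, and the SAP says it was not used. Nor would extending the rule give early detection: it fires in 7% of full cohorts at an assumed 30% rate and 74% at 70%.

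The conclusion rests on reading the criterion literally. A review team might apply Appendix 7 to SC reactions by analogy, but nothing in the text says so. The probabilities rest on the assumed rates and on no placebo reactions.

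**What to change.** In 3.4.2, replace the term infusion reaction with *systemic infusion- or injection-related reaction to investigational product (any route), graded by Appendix 7*. Keep the 50% and Grade 3 thresholds.

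In 7.1.13, state that:

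- systemic reactions after SC dosing are graded by Appendix 7, using the 7.1.12 time windows counted from administration of investigational product;
- reactions attributed to the vaccine challenge are excluded, since 1.6 lists fever and malaise among vaccine effects;
- local reactions stay under Appendix 8.

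An optional consistency edit is to reword the Grade 4 item in 3.4.3 so that it refers to the first dose and not the first infusion. SC subjects are already largely covered there by the SAE and Grade 3 bars.

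The cost is small but not zero. SAP 8.3.4 says the CRF recorded a toxicity grade for infusion-related events in place of the usual severity. SC systemic reactions would need the same grade, with an instruction to sites. An SC cohort could also be stopped by a rule that does not now reach it. No extra visits or subjects are needed.

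If dosing is already complete, as the actual doses in SAP Table 1 suggest, apply the route-neutral criterion descriptively to B1-B5 where grades can be assigned, and carry the wording into later protocols.
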